7.0 Study Procedures

Materials

Participants will receive Wyndmere Naturals, Inc. aromatherapy patches. The hydrogel adhesive patches are infused with essential oil for inhaled aromatherapy treatment. Wyndmere Naturals aromatherapy patches were chosen for the study because the produce (1) is not absorbed into the skin and (2) can be applied and changed by users. The aromatherapy patches provide an occlusive barrier that is hypoallergenic, allowing essential oils to be inhaled without coming in direct contact with the skin. Additionally, patches are easy to apply and change for users and the product has been used in a randomized control trial in which participants completed patch changes and documented in a symptom journal (Lillehei et al., 2015), similar to our protocol procedures. The patch manufacturer (Bioesse Technologies, LLC, Minnetonka, MN) recommends patch changes every 8 hours because the patch is time-released and can last for up to 8 hours.

Procedures

After consenting to study participation, patients will complete a brief demographic questionnaire (see Appendix A). Additional patient data (cancer type, chemotherapy regimen, transplant type, unit of hospitalization) will be collected from the electronic medical record by a study team member. Patients will be asked what symptom they find most concerning (nausea/vomiting or anxiety) and will then be randomly assigned to the intervention or control group using a random number table based on symptom of concern. After random assignment, the patient will be educated on how to use a symptom journal (Appendix B) by a study team member and will be asked to complete the baseline symptom measures in the journal. Patients will be instructed to complete the same symptom measures on the following day independently (24 hour follow up). Patients assigned to the intervention group will receive 48 hours (6 patches) worth of essential oil infused (lavender, peppermint, or mandarin) patches. Aromatherapy patches will be applied to the patient's skin containing peppermint, mandarin, or lavender essential oils. Patient indicating that nausea/vomiting is their symptom of concern will receive peppermint as the default oil or mandarin oil if they have a known intolerance to peppermint. Patients indicating that anxiety is their symptom of concern will receive lavender oil. Patients assigned to the control group will receive 48 hours (6 patches) worth of non-scented patches (i.e., blank hydrogel adhesive patches without essential oil infusion). Patients in both groups will be instructed to change the aromatherapy patch (essential oil infused [intervention group] or non-scented [control group]) every 8 hours, as recommended by manufacturer, and document the

patch change in the symptom journal. Patients in both groups will also be instructed to remove the aromatherapy patch and contact the study team with and signs/symptoms of sensitivity to the patch adhesive or essential oil. The study team will post an “aromatherapy in use” sign inside the patient room to notify clinicians that the patient is on study, with instructions to remove the aromatherapy patch before a MRI test.

The study team initial visit will be at 0 hours (visit 1) and follow-up visits will be completed at 24 hours (visit 2) and 48 hours (visit 3). During visit 2 (Monday-Friday only), the study team will remind participating patients to complete their symptom journal, will answer any study-related questions, and will inquire about any aromatherapy side effects. During visit 3, a study team member will instruct the patient to complete the 48-hour symptom measures in the journal and will complete a brief intervention satisfaction questionnaire (Appendix C) with the patient (intervention group only). Patients will be provided a \$25 gift card to show appreciation for their time in the study. After symptom data collection is completed, a study team member will review and document antiemetic medication administration from the electronic medical record during the 48-hour intervention time frame. **Antiemetic administration will be captured on an Excel spreadsheet on a secure Microsoft Team for intervention and control participants in the nausea/vomiting symptom group. Included medications are scopolamine, lorazepam, promethazine, prochlorperazine, olanzapine, dexamethasone, Marinol, and ondansetron indicated for nausea/vomiting. Medication type, dose, order type (scheduled vs. PRN), and number of doses will be documented for antiemetics administered during the study timeframe.** Concomitant medications (e.g., antiemetic medications, steroids, benzodiazepines) will not be controlled as part of the study as the intent is not to alter standard practice for symptom treatment, but rather to provide an adjuvant to help reduce symptom burden. However, it is reasonable to expect that the need for PRN (available as needed) medications prescribed for nausea/vomiting or anxiety may be less in the treatment group compared to control during the 48 hours of inhaled aromatherapy. Because antiemetic and benzodiazepine medications may contribute to an increase in fall risk (Seppala et al., 2018; Wildes et al., 2018), we also plan to observe fall events during the study timeframe. Unit fall total numbers and incidence data will additionally be obtained from data reported to the National Database for Nurse Quality Indicators (NDNQI) for 12 months prior to implementation and 12 months during study implementation.

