3.0 Outcome Measures

3.1 Primary Outcome Measures

Chemotherapy-Induced Nausea, Vomiting and Retching (CINVR)

CINVR involves three distinct gastrointestinal symptoms (nausea, vomiting, retching) influenced by administration of chemotherapy. Nausea is expressed as an unpleasant

feeling in the throat/epigastrium that can result in expulsion of stomach content, known as vomiting (Rhodes VA, 2001). Retching is the effort to expel stomach contents without success (Rhodes VA, 2001). A review of CINVR instruments identified the Rhodes Index of Nausea, Vomiting and Retching (INVR) was the only instrument that separately assesses all three symptoms (Wood et al., 2011). The INVR will be used to measure CINVR and includes 8 Likert-type items on a 5-point scale, with evidence supporting reliability (Spearman correlation 0.87) and validity (Rhodes & McDaniel, 1999). Completion of the tool will occur at baseline, 24 hour, and 48 hours of intervention.

The primary endpoint for CINVR is the mean INVR score change from (1) baseline to 24 hours and (2) baseline to 48 hours. We anticipate a 30% reduction in the INVR mean score for participants randomized to the intervention group who indicated nausea/vomiting as primary symptom of concern.

Anxiety

Anxiety is excessive or persistent worry about aspects of life ("Understanding the Facts of Anxiety Disorders and Depression is the First Step," n.d.). Anxiety will be measured using a shortened version of Spielberger's State Anxiety Inventory (SAI). The original SAI contains 20 items to measure state anxiety and items are scored using a 4-point Likert-type scale (almost never-almost always) (Spielberger, Gorsuch, Lushene, Vagg, & Jacobs, 1983). The SAI instrument has good internal consistency (.86-.95), test-retest reliability (.65-.75) (Spielberger et al., 1983), and evidence supporting construct and concurrent validity (Spielberger et al., 1983). The shortened SAI retains 6 items (from the original 20) and has evidence supporting good internal reliability consistency (Cronbach's alpha .84) and strong construct validity (Abed, Hall, & Moser, 2011). Completion of the tool will occur at baseline, 24 hours, and 48 hours of intervention.

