The primary endpoint for anxiety is the mean shortened SAI score change from (1) baseline to 24 hours and (2) baseline to 48 hours. We anticipate a 30% reduction in the SAI mean score for participants randomized to the intervention group who indicated anxiety as their primary symptom of concern.

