5.0 Study Design

This study will be a randomized controlled trial. Prior to randomization, participants will be asked which symptom, nausea/vomiting or anxiety, is most burdensome for them. Participants will be stratified based on their identified symptom of burden (nausea/vomiting or anxiety) and will then be randomized to either the intervention or control group, with a target of 50 participants in the nausea/vomiting symptom group (25 intervention and 25 control) and 50 participants in the anxiety symptom group (25 intervention and 25 control). Intervention and control groups will receive Wyndmere Naturals, Inc. aromatherapy patches and a symptom journal. Participants in the intervention group indicating that nausea/vomiting is the primary symptom of concern will receive peppermint inhaled aromatherapy patches (or mandarin if peppermint intolerance indicated). Participants in the intervention group indicating that anxiety is the primary symptoms of concern will receive lavender inhaled aromatherapy patches. The control group will receive non-scented aromatherapy patches (i.e., blank hydrogel adhesive patches without essential oil infusion), so it will not be feasible to blind participants to group assignment. The control group will have the same interactions with the study team as the intervention group and will complete patch changes and a symptom journal to serve as an attention control.

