6.0 Enrollment/Randomization

Potential participants will receive an information flyer and brief description of the study in clinic prior to stem cell transplant. Flyers will also be available in stem cell transplant classes. The

research team will evaluate the electronic medical record daily for patients meeting inclusion criteria for enrollment into the study on admission. Eligibility will be confirmed on admission and patients meeting inclusion criteria will be approached by the research team for potential study enrollment on post-transplant day 4, 5, 6, 7 or 8. Patients will be approached for potential study enrollment and if interested, will consent and begin study interventions post-transplant day 4, 5, 6, 7, or 8 (depending on day research team approaches). This timeframe will allow the team to observe for delayed CINVR and allow for flexibility in the study schedule to account for patient or study team member unavailability. The study team will provide a summary of the study and will review informed consent and HIPAA authorization documents. Patients that agree to participate in the study will sign a consent and HIPAA authorization. Consented participants will then be randomly assigned using a random number table generated in Microsoft Excel to allocate patients to the intervention or control group.

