12.0 Statistical Considerations

SAS and/or R statistical packages will be used to analyze primary outcomes, secondary outcomes, and demographic sample data.

Primary Outcomes

Comparisons between the intervention and control groups for differences in the CINVR and anxiety tools will be analyzed using mixed-model ANOVA, with time (baseline, 24 hours, 48 hours) repeated within subject. Chi-square tests will be used to compare the groups for differences in the proportions of patients prescribed medications for nausea/vomiting or anxiety. Separate analyses will be performed for the two symptom groups. A two-sided 5% significance level will be used for all tests.

Sample size justification: With sample sizes of 50 patients within each symptom group, 25 intervention/25 control within each symptom group, the study will have 80% power to detect an effect size of 0.81 between intervention and control within each symptom group, based on a two-sample t-test calculation and a two-sided 5% significance level. The recruitment target will be 112 participants (56 per symptom group) to account for a 10% drop out rate.

Secondary Outcomes

Descriptive statistics will be used to analyze frequencies and percentages of the patient satisfaction questionnaire responses, documented antiemetic administration, and number of unit falls. The number of (1) total antiemetic medication doses and (2) doses for each individual medication (i.e., Ativan, promethazine) will be compared between the control and intervention groups for the nausea/vomiting symptom group. The percentage change for number of falls will be calculated by comparing number of falls 12 months prior to intervention implementation to 12 months during implementation.

Descriptive statistics will be used to summarize the demographics of the study sample (frequencies and percentages for categorical variables, means and standard deviations for continuous variables).

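### The self-reported baseline is taken after random assignment, with nothing to keep the arm hidden until it is complete, and it enters all four primary change scores

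*Combined protocol and SAP*

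**What the plan says.** Section 7.0 (Procedures) gives the order of Visit 1. The patient names the symptom of most concern and "will then be randomly assigned to the intervention or control group using a random number table based on symptom of concern". The next sentence reads "After random assignment, the patient will be educated on how to use a symptom journal" and goes on to say that the patient "will be asked to complete the baseline symptom measures in the journal". Supply of the scented or blank patches is described after that.

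Section 6.0 also moves from consent to assignment with no baseline assessment in between: "Consented participants will then be randomly assigned using a random number table generated in Microsoft Excel". Section 5.0 explains that the control patch is unscented, "so it will not be feasible to blind participants to group assignment". The Section 8.0 calendar puts consent, symptom tools and patch application in Visit 1, but it has no randomisation row.

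Section 3.1 defines the endpoints as change from this baseline: "The primary endpoint for CINVR is the mean INVR score change from (1) baseline to 24 hours and (2) baseline to 48 hours" and "The primary endpoint for anxiety is the mean shortened SAI score change from (1) baseline to 24 hours", with the 48-hour change added for anxiety as well. Section 12.0 analyses both instruments by "mixed-model ANOVA, with time (baseline, 24 hours, 48 hours) repeated within subject".

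**The concern.** The INVR and the shortened SAI are self-reports. A patient who has just learned that the patch will be scented, or blank, may rate current nausea or anxiety differently because of that news. Randomisation protects the comparability of a baseline only if the arm cannot influence it. A baseline reported after the arm is known loses that protection.

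Any shift between arms would pass into all four primary change scores (INVR and SAI, each at 24 and 48 hours) and into the repeated-measures model, where baseline is an outcome level. It could create an apparent effect or hide a real one. Adjusting for baseline would reduce a baseline-only shift without removing it, because the covariate is itself affected. Comparing follow-up scores alone would avoid the baseline shift but would abandon the stated change endpoint.

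The point concerns disclosure of the arm, not exposure to the patch. Section 7.0 describes the baseline measures before the patches are supplied.

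**Working it through.** **The order of events.** Section 7.0 gives: symptom of concern, random assignment, journal teaching, baseline measures, patches. Section 6.0 is consistent with this, and the Section 8.0 calendar neither confirms nor corrects it. No section states when the patient learns the arm, and none conceals it until the baseline is complete. So the written order permits an informed baseline but does not prove that one occurs.

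**The plan's own figure.** Inputs from Section 12.0: 25 per arm in each symptom group, effect size 0.81, two-sided 5%, two-sample t-test. The noncentrality is 0.81 × √(25/2) = 2.86 on 48 df, which gives power 80.1%. The stated 80% is reproduced. Dropout: 50/0.9 = 55.6, so 56 per symptom group and 112 in total, also as stated. Neither figure is in dispute.

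**What a shift would do.** The documents give no size for a shift, so these inputs are assumptions: a spurious between-arm difference *s* of 0.1, 0.2 or 0.3 single-time SD, present at baseline only; correlation ρ of 0.3 to 0.7 between times, with compound symmetry; no true effect; 25 per arm.

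- (a) t-test on one change score: the change has SD √(2(1−ρ)), so the noncentrality is [s/√(2(1−ρ))] × √12.5 on 48 df. For s = 0.2 and ρ = 0.5 this is 0.2 × 3.536 = 0.707, and the rejection rate is 10.7%.
- (b) Mixed model, group-by-time F(2, 96): noncentrality 12.5 × (2/3) × s²/(1−ρ). For s = 0.2 and ρ = 0.5 this is 0.667, and the rate is 10.2%.
- (c) Mixed model, group main effect: difference s/3, SD √((1+2ρ)/3), 48 df. For s = 0.2 and ρ = 0.5 the rate is 5.9%.
- (d) ANCOVA: residual bias ρs, residual SD √(1−ρ²), 47 df.

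False-positive rates against a nominal 5%, over ρ = 0.3 to 0.7:

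| Test | s = 0.1 | s = 0.2 | s = 0.3 |
|---|---|---|---|
| (a) change t-test | 6.0–7.3% | 9.0–14.6% | 14.2–26.9% |
| (b) group-by-time | 5.9–7.1% | 8.6–14.0% | 13.6–26.6% |
| (c) group main effect | 5.2–5.3% | 5.8–6.2% | 6.7–7.6% |
| (d) ANCOVA | – | 5.5–10.4% | – |

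Section 12.0 does not say whether (b) or (c) is the primary test.

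**If the shift persists.** Only the part that does not carry over to follow-up affects a change score. If half of a 0.2 SD shift persists, the net shift is 0.1 SD and (a) falls to 6.0–7.3%. If all of it persists, the net shift is zero and the rate is 5.0%.

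**If the shift opposes a true effect.** Section 12.0 does not say which SD the 0.81 uses. Read as SDs of the change score, 0.2 single-time SD equals 0.2/√(2(1−ρ)) = 0.17, 0.20 or 0.26 change-SD for ρ = 0.3, 0.5 or 0.7. That is 21%, 25% or 32% of 0.81. Power falls from 80.1% to 60.3%, 56.1% or 48.1%. An opposing shift of 0.1 SD leaves 65.5–71.0%.

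**The case against.** The strongest reply has three parts.

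First, exposure is inferred. Section 7.0 describes handing over the patches after the baseline, so the patient might learn the arm only then. The remark on blinding in Section 5.0 gives the unscented patch as its reason and may refer to wearing it. This stands in part: early disclosure is possible, not certain. What remains is that assignment is written before the baseline and no safeguard is stated. If the arm is in fact withheld, one sentence would say so.

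Second, the larger error rates need a shift that appears at baseline and is gone by 24 hours. The same unblinded patient fills in the same forms later, so persistence is at least as plausible, and the rate then moves back towards 5%. The group main effect is barely affected in any case. This stands. The rates are illustrations under assumptions, not estimates of harm in this trial.

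Third, the fix has a price. If knowing the arm shifts reporting by a constant 0.2 SD, the present order cancels that shift in the change score. With a clean baseline it would appear at follow-up only, and the change t-test would reject at the same 9.0–14.6%. The arithmetic is right, so the fix need not lower total bias under every scenario. It is still not a reason to keep the present order, because relying on two unknown biases to cancel is no design safeguard. Unblinded follow-up is hard to avoid with a scented patch; an unblinded baseline is easy to avoid.

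**Conclusion.** The concern holds and should be fixed. The plan places a subjective baseline after random assignment in a trial whose participants cannot be blinded, and it states no rule that keeps the arm hidden until the baseline is complete. Confidence is high on the written order and the missing safeguard. Whether bias actually occurs, and in which direction, cannot be told from the documents.

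The practical size runs from nothing (a shift that persists fully) to a material loss of error control or power (a shift of 0.2 SD or more confined to baseline and tested on change or group-by-time). The stated sample size and power are unaffected as calculations.

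**What to change.** Rewrite Sections 6.0 and 7.0, and order the Visit 1 rows of the Section 8.0 calendar with a randomisation row added, so that the sequence is:

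1. Consent.
2. Demographic questionnaire.
3. Symptom of concern, which is all that stratification needs.
4. Brief instruction on the measures.
5. Baseline INVR and SAI completed, on the journal's baseline page or a separate copy, and checked by the study team.
6. Only then, draw and disclose the arm, give the patch instructions and apply the first patch.

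State in Section 7.0 that the arm is neither drawn nor disclosed until the baseline has been checked as complete. The sample journal page in Appendix B has a field for the oil beside the measurement tool; under this order it is necessarily blank at baseline.

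If any patient's baseline followed disclosure, record that. Add a sensitivity comparison of the 24-hour and 48-hour scores that does not use baseline, run in all randomised patients with those scores so that no subset is selected after randomisation.

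The cost is minor rewording and possibly one extra page. Sample size, visits and staff do not change. The report should acknowledge separately that the 24-hour and 48-hour scores are unblinded self-reports, and that a reporting shift there would no longer be partly offset by the same shift at baseline.

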4.2 Exclusion Criteria

- Under 18 years of age
- Currently receiving another form of essential oils (e.g., diffuser, essential oil roller, lotion with essential oils) within 24 hours of enrollment
- Intubation
- Medical sedation
- Receipt of chimeric antigen receptor T (CAR-T) cells
- History of atrial fibrillation
- History of seizures/epilepsy
- Adhesive allergy or sensitivity
- Currently pregnant
- Prisoner
- Inability to smell

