9.0 Reportable Events

Inhaled essential oils including lavender, peppermint, and mandarin are generally considered safe if used as indicated. The essential oils used in this study are infused within an adhesive patch, so will not come in direct contact with the skin. However, if the essential oil patch is used not as indicated (e.g. oil applied directly to the skin, oil ingested), the risk of adverse event occurrence may increase.

Adverse Event: Defined as any problematic medical occurrence in a study participant who has received the intervention including inhaled lavender, peppermint, or mandarin essential oil, regardless of possibility of a causal relationship. Adverse events will be documented after the participant begins receiving the intervention.

The occurrence and nature of each participant's medical condition will be documented by study personnel prior to enrollment. Study personnel will document any changes in medical condition and/or the occurrence and description of any adverse event during the study. Events that occur from inhaled essential oil administration up to 72 hours after will be recorded (allows for 24 hours of monitoring after intervention ends). Events will be reviewed during data safety monitoring to determine causality.

Significant Adverse Event: Defined as a life-threatening condition (i.e. immediate risk of dying); severe/permanent disability; a significant hazard, contraindication, side effect, or precaution as deemed by the Data Safety Monitoring team to be caused by the intervention. Investigators will determine causality based on the participant's clinical course, medical history, and administered medications.

Adverse and Significant Adverse Events will be reported to the IRB within 5 business days from discovery if they are determined to be (1) unexpected; (2) related or possibly related to participation in the study; (3) finding suggests that the research procedures involve a greater harm risk than previously anticipated; (4) occurrence of unanticipated adverse device effects.

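### Known intolerance to a study oil is not an exclusion and only peppermint has a substitute, so a lavender-intolerant anxiety patient can be assigned lavender (minor safety gap, cheap to close)

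*Combined protocol and SAP*

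**What the plan says.** Three parts of the combined protocol and SAP bear on this.

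- **Eligibility (4.2).** The list excludes "Adhesive allergy or sensitivity". Its other entries on oils or smell cover recent use of other essential oils and the inability to smell. No entry covers allergy or intolerance to a study oil.
- **Oil for nausea/vomiting (5.0 and 7.0).** Intervention patients "will receive peppermint inhaled aromatherapy patches (or mandarin if peppermint intolerance indicated"). Section 7.0 repeats the rule: they "will receive peppermint as the default oil or mandarin oil if they have a known intolerance to peppermint".
- **Oil for anxiety (5.0 and 7.0).** "Patients indicating that anxiety is their symptom of concern will receive lavender oil". Neither section gives an exception.

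Other provisions limit the risk. Section 9.0 has each participant's "medical condition will be documented by study personnel prior to enrollment" and describes the inhaled oils as "generally considered safe if used as indicated". Section 7.0 describes the patch as a barrier "allowing essential oils to be inhaled without coming in direct contact with the skin". Section 5.0 accepts that "it will not be feasible to blind participants to group assignment". Patients in both arms are told to take the patch off and call the team if they react to the adhesive or the oil. A sign in the room tells clinicians that the patient is on study (7.0), and participants may withdraw at any time (11.0).

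**The concern.** The plan screens for intolerance to the patch material but not to the oil in it. It provides for intolerance to one of its two default oils and is silent on the other. A patient who already knows that lavender does not agree with them, and who names anxiety as the main burden, passes every criterion in 4.2. If randomised to intervention, that patient is assigned lavender. A nausea/vomiting patient who tolerates neither peppermint nor mandarin is in the same position.

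The first stake is participant safety: an avoidable exposure of up to 48 hours in people recently transplanted. The second is procedural. If the intolerance surfaces only after assignment, staff have no rule to follow. They would have to improvise a change or a withdrawal, and that would happen only in the lavender arm of an open-label trial, since control patients receive blank patches.

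This is an omission and not a contradiction between sections. The protocol neither defines intolerance nor says why mandarin is offered, so the peppermint rule is not proof of a recognised hazard.

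**Working it through.** **Reading the rules in order for an anxiety patient with known lavender intolerance**

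1. Inclusion and exclusion (4.1, 4.2): no visible criterion is failed, so the patient is eligible.
2. Symptom named (5.0, 7.0): anxiety.
3. Random number table (6.0, 7.0): intervention, with 1:1 allocation.
4. Oil rule (5.0, 7.0): lavender, without exception.

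Pre-enrolment documentation, consent and the study summary could bring the intolerance to light. None is tied to a rule that excludes the patient or changes the oil. Patch removal and the visit 2 enquiry about side effects (Monday to Friday only) act after exposure. The barrier prevents skin contact, but inhalation is the intended route.

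**The plan's own figures (12.0)**

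- Inputs: 25 per arm, effect size 0.81, two-sided 5%, two-sample t-test. Noncentral-t power is 80.1%, which agrees with the stated 80%.
- Dropout: 50/(1 − 0.10) = 55.6, rounded up to 56 per symptom group, or 112 in total. Per arm within a symptom group: 112/4 = 28.

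**Size of the gap**

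The documents give no frequency, so p, the proportion of anxiety patients with known lavender intolerance, is assumed to lie between 0.5% and 5%. The formulas are:

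- upper-bound expected number assigned lavender = 28p, which supposes that nobody is caught or declines;
- chance of at least one = 1 − (1 − p)^28;
- the same two quantities with p/2 in place of p, if half are caught by existing steps or decline (also an assumption);
- number to screen to randomise 56 once the exclusion is added = 56/(1 − p);
- power at 25 per arm with the effect diluted to 0.81(1 − p), that is, with the whole effect lost in every such patient.

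| p | 28p | Chance of ≥1 | 28(p/2) | Chance of ≥1 | Screened for 56 | Diluted effect | Power |
|---|---|---|---|---|---|---|---|
| 0.5% | 0.14 | 13% | 0.07 | 7% | 56.3 | 0.806 | 79.7% |
| 1% | 0.28 | 25% | 0.14 | 13% | 56.6 | 0.802 | 79.3% |
| 2% | 0.56 | 43% | 0.28 | 25% | 57.1 | 0.794 | 78.5% |
| 5% | 1.40 | 76% | 0.70 | 51% | 58.9 | 0.770 | 76.0% |

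The nausea/vomiting patient intolerant of both oils is not sized. That would need a joint frequency, for which the documents offer no basis.

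**The case against.** The strongest reply is that this is a drafting preference. The documents do not identify lavender intolerance as a hazard, and section 9.0 regards the oils as safe in proper use. Participants are alert, hear a summary, consent and know what they are given. Someone who knows that lavender does not suit them can say so or decline. Exposure lasts 48 hours from a patch the patient can remove, adverse events are recorded to 72 hours (9.0), and the team reviews weekly with scope to adjust the protocol (10.0). The consent pages are not in the reviewed text and may carry an allergy warning. A figure in 4.1 is not visible either. The frequencies are assumptions, and the 76% chance merely restates the 5% rate. Finally, the symptom is named only after consent, so a criterion tied to symptom group creates a post-consent screen failure that sections 6.0 and 8.0 do not provide for.

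Much of this stands as a limit on importance. The severity of harm cannot be sized, the frequencies have no source, and the upper bound does suppose that intolerant patients enrol and stay silent. The post-consent screen failure is a real cost, though a very small one. The reply does not remove the omission. The safeguards act after exposure, or might surface the intolerance without saying what to do next. A consent warning could reduce the practical risk but would not amend 4.2 or the oil rules. The missing figure sits under inclusion, not in the exclusion list.

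**Conclusion.** The concern holds, as a minor point. On the visible text, the eligibility and oil-assignment rules together allow lavender to be given to a patient known not to tolerate it. This follows from reading the sections side by side and does not depend on the assumed frequencies.

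The frequencies matter only for size. With 0.5% to 5% assumed, at most 0.14 to 1.4 such patients are expected in the lavender arm, or 0.07 to 0.7 if half are caught beforehand. Power stays between 76% and 80%, so the effect on the randomised comparison is negligible and the case for change rests on participant safety and on avoiding improvised changes after randomisation in one arm. Confidence is medium, because neither the frequency nor the severity of reactions to an inhaled oil can be taken from the documents. The change is worth considering because it costs so little.

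**What to change.** Add one line to 4.2: *Known allergy or intolerance to every study oil offered for the patient's symptom group.* State what counts as intolerance, since the protocol leaves the term undefined. This wording keeps mandarin available to a patient intolerant of peppermint alone.

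Ask every patient about lavender, peppermint and mandarin, by the record-review or self-report route already set out in 4.0. The question can be put at admission screening or at visit 1. Apply the answer after the symptom is named and before the random number table is used, so that both arms are screened alike. Note in 6.0 and 8.0 that a patient may fail screening at this step after consent. The sponsor may prefer to name a substitute for lavender instead.

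The cost is one criterion and one question, with no change to endpoints, analysis or sample size. Over the assumed range, 0.3 (56.3 − 56) to 2.9 (58.9 − 56) more anxiety patients would have to be screened to randomise 56.
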